Secondary Efficacy Endpoints	The secondary efficacy endpoint will be the proportion of subjects exhibiting a relative decrease of 25% or more inflammation between the baseline kidney biopsy and the biopsy 2 weeks after polyTregs, measured as the percentage area of cortex occupied by inflammatory cells using computer-assisted quantitative image analysis. Additional secondary efficacy endpoints are the number of subjects who exhibit a relative decrease of 50% or more inflammation on kidney biopsy at 2 weeks after polyTregs; and the proportion of subjects who exhibit a relative decrease of 25% or more inflammation at 7 months after group allocation.
Primary Mechanistic Endpoint	The primary mechanistic endpoints are the immunologic profiles of kidney transplant recipients using graft CRM (common response module) gene expression of rejection and/or evidence of inflammation in biopsies at 2 weeks after infusion (Group 2) and 7 months after group allocation (Groups 1 and 2).
Secondary Mechanistic Endpoints	The secondary mechanistic endpoints are the immunologic profiles of kidney transplant recipients using: 
 1. Persistence of infused Tregs in blood and biopsies using deuterium labeling and T cell repertoire analysis (Group 2) 2. Cytokine and CRM (common response module) mRNA and protein profiles in the urine as correlates of acute rejection and/or histologic evidence of inflammation and graft fibrosis (Groups 1 and 2) 3. Peripheral blood kSORT (kidney solid organ response test) mRNA expression of rejection/increased immune response (Groups 1 and 2)
Accrual Objective	14 Subjects Total: 7 subjects on CNI maintenance therapy 7 subjects to receive polyTregs
Study Duration	6.5 Year Accrual, 12 Months Follow Up
Treatment Description	Subjects will be on maintenance IS therapy using CNI + MMF/MPA with or without steroids at the time of study entry. Eligible subjects will be randomized to receive: 
 1. Standard CNI maintenance IS (no Tregs) 2. $550 \pm 450 \times 10^6$ polyTregs After receiving at least 300×10^6 polyTregs infusion, eligible subjects will start mTOR inhibitor.

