3.3.2 Secondary Safety Endpoint for mTOR Therapy

The safety of mTOR therapy after Treg infusion will be assessed by the timing and incidence of acute rejection in Group 2. Subjects who receive Tregs and convert to mTOR therapy will be compared to subjects who did not convert to mTOR therapy; as well as subjects in group 1.

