4.1.2 Exclusion Criteria

Individuals who meet any of these criteria are not eligible for enrollment as study participants:

1. Inability or unwillingness of a participant to give written informed consent or comply with study protocol
2. History of malignancy; except adequately treated basal cell carcinoma
3. History of graft loss from acute rejection within 1 year after any previous transplant
4. History of transplant renal artery stenosis
5. History of cellular rejection prior to enrollment that did not respond to steroids and/or subsequent creatinine after treatment for rejection greater than 15% above baseline
6. Known hypersensitivity to mTOR inhibitors or contraindication to everolimus (including history of wound healing complications)
7. Any chronic illness requiring uninterrupted anti-coagulation after kidney transplantation
8. Post-transplant DSA >5000 MFI or post-transplant treatment with IVIg for DSA. Enrolled subjects with post-transplant DSA >2000 MFI will not be eligible for mTOR conversion.
9. Positive HIV 1 or HIV 2 serology prior to transplantation
10. Known positive HBSAg, or HBcAB serology
11. Proteinuria with urine pr/cr > 1.0 g/g
12. Any condition requiring chronic use of corticosteroids >10mg/day at the time of study entry
13. Subjects requiring treatment for pathologic findings on study eligibility biopsy (see inclusion 4).
14. Active infection at the time of study entry
15. History of active TB or latent TB without adequate treatment (see inclusion 10)
16. Serum BK virus >1,000 copies/ml by PCR at the time of study entry
17. Hematocrit <27%; ANC < 1,000/ μ L; lymphocytes <500/ μ L at the time of study entry
18. Participation in any other studies with investigational drugs or regimens in the preceding year
19. Any condition or prior treatment which, in the opinion of the investigator, precludes study participation
20. Unable to provide adequate biopsy specimen (paraffin embedded formalin fixed) from eligibility biopsy (3-7 months post-transplant) for quantitative analysis.
21. EBV naïve recipient of a kidney from an EBV positive donor, historically EBV naïve recipient with primary EBV infection at the time of screening (primary anti-VCA IgM, without antibody to EBNA), positive EBV PCR
22. Hepatitis C Virus Ab positive subjects with negative HCV PCR are eligible if they have spontaneously cleared infection or are in sustained virologic remission for at least 12 weeks after treatment.
23. Positive SARS-CoV2 testing by RT- PCR

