4.2.2. Treg Infusion Exclusion Criteria

Individuals randomized to group 2 who meet any of these criteria are not eligible for Treg infusion:

1. Received any vaccination within 14 days prior to blood collection for Treg manufacture
2. Unacceptable Treg product
3. Positive pregnancy test for women of childbearing potential

4.3. mTOR Conversion Eligibility Criteria

4.3.1. mTOR Conversion Inclusion Criteria

Individuals who meet all of these criteria are eligible for mTOR conversion:

1. Received at least 300×10^6 polyTreg infusion
2. Resolution of inflammation on the 2-week post-infusion biopsy as compared to the baseline biopsy, confirmed by central pathologist

4.3.2 mTOR Conversion Exclusion Criterion

Individuals who meet any of these criteria are not eligible for mTOR conversion:

1. Post-transplant DSA >2000 MFI
2. Any condition or clinical variable, which in the opinion of the site investigator, precludes conversion to mTOR.

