15.3.2. Endpoint Assessments

15.3.2.1 Primary and Secondary Safety Endpoints

Table 7. Analyses of Safety Endpoints describes the safety endpoints and their corresponding parameters to be estimated in the study. Safety endpoints will be listed or summarized, as appropriate, using standard descriptive statistics for continuous and categorical data.

Table 7. Analyses of Safety Endpoints

ENDPOINT	DESCRIPTIVE PARAMETER	ANALYSIS POPULATION
Primary Endpoint		
Incidence of severe acute rejection or antibody mediated rejection in subjects receiving polyTregs in comparison with CNI-based maintenance IS therapy.	Proportion with exact binomial 95% confidence limits	miITT1
Incidence of severe infection in subjects receiving polyTregs in comparison with CNI-based maintenance IS therapy.	Proportion with exact binomial 95% confidence limits	miITT1
Secondary Endpoints – Treg safety		
Incidence of polyTregs infusion reactions (episodes of fever, bronchospasm, hypoxia, cytokine release syndrome, or infusion site reaction)	Proportion with exact binomial 95% confidence limits	miITT2
Severity of polyTregs infusion reactions	Descriptive CTCAE categories	miITT2
Incidence of culture-proven and clinically diagnosed infections	Proportion with exact binomial 95% confidence limits	miITT1
Severity of culture-proven and clinically diagnosed infections	Descriptive CTCAE categories	miITT2
Incidence of severe infection in subjects receiving polyTregs in comparison with CNI-based maintenance IS therapy.	Proportion with exact binomial 95% confidence limits	miITT1
Timing of acute rejection	Mean time to rejection and standard deviation	miITT1
Incidence of acute rejection	Proportion with exact binomial 95% confidence limits	miITT1
Severity of acute rejection	Descriptive Banff criteria	miITT1
Incidence of CMV reactivation	Proportion with exact binomial 95% confidence limits	miITT1
Incidence of BK viremia	Proportion with exact binomial 95% confidence limits	miITT1
Incidence of >10% decrease in eGFR from baseline	Proportion with exact binomial 95% confidence limits	miITT1
Secondary Endpoints – mTOR therapy		
Incidence of acute rejection	Proportion with exact binomial 95% confidence limits	miITT2 (Treg mTOR vs Treg no mTOR)

15.3.2.2 *Supportive Analyses of the Primary Safety Endpoints*

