### **8.2.1. Endpoints**

**Variable:** Secondary incidence endpoints including:

Endpoint	Time Frame
polyTreg infusion reactions	405 days post-group allocation
Culture-proven and clinically diagnosed infections	405 days post-group allocation

Acute rejection using Banff grading	405 days post-group allocation
BK viremia after polyTregs infusion	405 days post-group allocation
CMV reactivation after polyTregs infusion	405 days post-group allocation
>10% decrease in eGFR compared to baseline	405 days post-group allocation
Acute rejection after converting to mTOR therapy after polyTregs infusion	69 days post-group allocation to 405 days post-group allocation
Proportion of participants exhibiting $\geq 25\%$ decrease of inflammation between baseline kidney biopsy and the week 2 kidney biopsy	Baseline biopsy to Week 2 kidney biopsy
Proportion of participants exhibiting $\geq 50\%$ decrease of inflammation between baseline kidney biopsy and the week 2 kidney biopsy	Baseline biopsy to Week 2 kidney biopsy
Proportion of participants exhibiting $\geq 25\%$ decrease of inflammation between baseline kidney biopsy and the month 6 kidney biopsy	Baseline biopsy to 6 month kidney biopsy (for polyTregs infusion group). Baseline biopsy to 7 months post-group allocation (for maintenance therapy group).

**Analysis:** For each of the above incidence endpoints, the proportion of participants with events will be reported by treatment group and compared using Fisher's Exact test or a Cochran-Mantel-Haenszel test.

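### The mTOR safety endpoint contrasts converters, selected partly on resolved inflammation, with non-converters: the contrast is plausibly confounded in favour of conversion, and the SAP adds between-group tests that the protocol rules out

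*Protocol*

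**What the plan says.** Protocol 3.3.2 assesses mTOR safety by the timing and incidence of acute rejection: "Subjects who receive Tregs and convert to mTOR therapy will be compared to subjects who did not convert to mTOR therapy". The same sentence adds Group 1 as a comparator. The Protocol Synopsis and SAP section 3 name the same two comparators.

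Conversion is decided by four conditions:
- Histology (Protocol 4.3.1): "Resolution of inflammation on the 2-week post-infusion biopsy as compared to the baseline biopsy, confirmed by central pathologist". Section 6 leaves the regimen unchanged if any inflammation persists, even if it is reduced.
- Cell dose (Synopsis and 4.3.1): a minimum of 300 x 10^6 cells applies before the rule that after "polyTregs infusion, eligible subjects will start mTOR inhibitor". Section 5.3 allows infusion from 100 x 10^6.
- Antibody (4.1.2): "Enrolled subjects with post-transplant DSA >2000 MFI will not be eligible for mTOR conversion". Trial entry allows DSA up to 5000 MFI.
- Judgement (4.3.2): "Any condition or clinical variable, which in the opinion of the site investigator, precludes conversion to mTOR".

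Protocol Table 7 gives this endpoint a proportion with exact binomial limits in the population "miITT2 (Treg mTOR vs Treg no mTOR". Group 1 does not appear there. Section 15.5 says that secondary endpoints will be described and not statistically compared between groups.

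SAP 8.2.1 lists "Acute rejection after converting to mTOR therapy after polyTregs infusion" with a window of day 69 to day 405 after allocation, in mITT2. It compares incidence by Fisher's exact or Cochran-Mantel-Haenszel test, and timing by ANOVA, Kruskal-Wallis or t-test. It names no strata and no covariates.

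**The concern.** The two Group 2 subsets differ by design before anyone takes everolimus. Converters have resolved inflammation, a dose above the threshold and lower DSA. Non-converters include everyone with persisting inflammation and everyone with DSA above 2000 MFI. If these features bear on rejection, converters would reject less even if nobody's regimen changed. A harm from withdrawing tacrolimus is then set against a head start. For a safety endpoint this is the wrong direction for an error, because a reassuring result could come from selection alone. Neither document adjusts for this or warns of it.

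Two features of the SAP make it worse. A p-value on this contrast invites a non-significant result to be read as safety. And a window counted from allocation does not measure rejection after conversion.

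**Working it through.** **1. The plan's own figures.** Neither document gives an event rate, power or precision for this endpoint. The only power figures (Protocol Table 11) concern primary efficacy and have no bearing here. All risks below are assumptions, shown over a range.

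**2. Size of the distortion.** Let S be the rejection risk on continued tacrolimus in those eligible to convert, divided by that in non-converters. Let T be the true risk ratio of conversion. The apparent ratio is S x T.

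| | S = 0.25 | S = 1/3 | S = 0.5 | S = 0.75 | S = 1 |
|---|---|---|---|---|---|
| T = 1.5 | 0.38 | 0.50 | 0.75 | 1.12 | 1.5 |
| T = 2 | 0.50 | 0.67 | 1.0 | 1.5 | 2.0 |
| T = 3 | 0.75 | 1.0 | 1.5 | 2.25 | 3.0 |

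Worked case for S = 1/3 and T = 2: risk on tacrolimus is 10% if eligible and 30% if not. Conversion doubles 10% to 20%. The contrast shows 20% against 30%, a ratio of 0.67 and a difference of -10 points, where the true difference is +10 points. With 3 converters and 4 non-converters, exact enumeration gives converters the lower observed rate with probability 0.53, a tie 0.12 and the higher rate 0.35.

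**3. Group 1 as comparator.** Only Group 2 has a week-2 biopsy (Protocol 8.3), so Group 1 cannot be restricted to those who would have met the histology criterion. If a share s of Group 1 would have, its risk is 10% x s + 30% x (1 - s). For s = 0.25, 0.5 and 0.75 this is 25%, 20% and 15%. Converters at 20% then show ratios of 0.8, 1.0 and 1.33, against a true 2.0.

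**4. What a test on 7 people can show.** The smallest two-sided Fisher p, reached when all of one subset and none of the other reject, is:
- 4:3 split: 1/C(7,3) = 1/35 = 0.029
- 5:2 split: 1/C(7,2) = 1/21 = 0.048
- 6:1 split: 1/C(7,1) = 1/7 = 0.143

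Any less extreme table exceeds 0.05. With 3 converters at a true 30% and 4 non-converters at 10%, the chance of the significant table is 0.3^3 x 0.9^4 = 0.018. For precision, 0/3 rejections has an exact upper 95% limit of 1 - 0.025^(1/3) = 70.8%, and 0/7 has 41.0%.

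**5. The day-69 window.** Everolimus starts within 2 weeks of the week-2 biopsy (Protocol 6.1.3).
- Nominal timing: the Group 1 schedule places the infusion-equivalent visit at day 41. The biopsy is then at 41 + 14 = day 55, with conversion between day 55 and day 69. Rejection after a day-55 conversion but before day 69 is not counted.
- Early: if blood is collected on the day of allocation (assumed possible) and infusion follows 16 days later (Appendix 4), the biopsy is at day 30 and conversion can start then.
- Late: infusion may be up to day 62 after central confirmation (10.3.2). If allocation is on the day of confirmation, the biopsy is at day 76 and conversion can be as late as day 90. Days 69 to 90 then precede conversion, and a rejection in that gap that prevents conversion would count against non-converters.

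**The case against.** The strongest reply is that the protocol already calls this descriptive. Section 3.1 speaks of describing mTOR safety, Table 7 asks for a proportion with exact limits, section 15.5 disclaims between-group comparison, and SAP 7.1.4 calls the analysis primarily descriptive. That stands, and it lowers the weight of the point. It does not settle it: SAP 8.2.1 still specifies tests, SAP section 10 does not declare them as a change, and a descriptive side-by-side of differently selected groups still misleads without a caveat.

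Four stronger readings are tempting but not supported:
- That non-converters are the only comparator. Protocol 3.3.2 also names Group 1. The problem is that Table 7 and the SAP population leave it out.
- That the SAP expressly tests converters against non-converters. It compares by treatment group, yet restricts the endpoint to mITT2, which holds one treatment group. Read with Table 7 and SAP section 3, converters against non-converters is the most plausible meaning, but the text is ambiguous.
- That the protocol shows persisting inflammation raises acute rejection. Section 2.1.2 gives subclinical inflammation and borderline change the same potential for alloimmune damage as clinical rejection, but the outcomes it cites are mainly chronic injury, function and graft survival. The link to rejection incidence is plausible, not documented.
- That participants' safety rests on this contrast. Rejection on everolimus triggers a protocol action (6.4), rejections are reported within 24 hours (14.2.4), and the medical monitor and DSMB review safety data (14.8).

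**Conclusion.** The point holds as a matter of interpretation and SAP wording. Selection into conversion is documented, unadjusted and without a caveat, and plausibly favours conversion. How far is unknown. For a true ratio of 2, the apparent ratio is 0.67, 1.0 or 1.5 at assumed selection ratios of 1/3, 0.5 or 0.75. A reader might infer that harm will be made to look like protection, or that the objective will be answered wrongly. The documents do not support that: reversal needs S x T below 1, and with 7 infused the endpoint cannot support a firm conclusion either way. Group 1 does not cure the confounding, the planned test is nearly empty, and the fixed window does not measure rejection after conversion. Because this is a secondary endpoint in a self-described pilot, the weight is minor to should-fix.

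**What to change.** - In SAP 8.2.1, remove the between-group tests of incidence and timing for this endpoint, in line with Protocol 15.5.
- Report converters as n/N with exact 95% limits, and give follow-up time from each person's first everolimus dose in place of the day 69 to 405 window.
- List non-converters, with the reason for not converting (histology, cell dose, DSA, investigator judgement), and Group 1 alongside without a test. State the time origin used for each.
- Reconcile Protocol 3.3.2 and SAP section 3, which include Group 1, with Protocol Table 7 and the SAP 8.2.1 populations, which do not.
- State in Protocol 3.3.2 and the SAP that converters were selected on response, so a lower or equal rejection rate is not evidence that conversion is safe.

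No conversion rule changes. The cost is wording and the loss of uninformative p-values for this endpoint. The objective becomes openly descriptive, which Protocol 15.5 already intends.

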3.4. Primary Efficacy Endpoint

The primary efficacy endpoint will be the change in inflammation as measured by the percentage area of cortex occupied by inflammatory cells using computer-assisted quantitative image analysis on the biopsy 7 months after study group allocation, expressed as the percent change relative to the baseline biopsy.

3.5. Secondary Efficacy Endpoints

The secondary efficacy endpoint will be the proportion of subjects exhibiting a relative decrease of 25% or more inflammation between the baseline kidney biopsy and the biopsy 2 weeks after polyTregs, measured as the percentage area of cortex occupied by inflammatory cells using computer-assisted quantitative image analysis.

Additional secondary efficacy endpoints are the proportion of subjects who exhibit a relative decrease of 50% or more inflammation on kidney biopsy at 2 weeks after polyTregs; and the proportion of subjects who exhibit a relative decrease of 25% or more inflammation at 7 months after study group allocation.

3.6. Primary Mechanistic Endpoints

The primary mechanistic endpoints are the immunologic profiles of kidney transplant recipients using the common response module (CRM) graft gene expression of rejection and/or histologic evidence of inflammation in biopsies at 2 weeks after infusion (Group 2) and 7 months after study group allocation (Groups 1 and 2).

3.6.1. Secondary Mechanistic Endpoints

The secondary mechanistic endpoints are the immunologic profiles of kidney transplant recipients using:

1. Persistence of infused Tregs in blood and biopsies using deuterium labeling and T cell repertoire analysis (Group 2)
2. Cytokine and CRM mRNA and protein profiles in the urine as correlates of acute rejection and/or histologic evidence of inflammation and graft fibrosis (Groups 1 and 2)
3. Peripheral blood (kidney solid organ response test) kSORT mRNA expression of rejection/ increased immune response (Groups 1 and 2)

3.7. Stratification, Study Group Allocation, and Blinding/Masking

This is an open label, parallel group study in which subjects are assigned to treatment alternatives in an unblinded fashion using a variation of the Pocock and Simon adaptive randomization strategy. A web-based randomization system will be used in order to minimize the possibility of bias entering into those assignments and to maintain approximate equality in the group sizes. The initial treatment allocation will weight each treatment equally. In subsequent allocations, the less-populated arm will be weighted more in order to restore the balance between the groups. If a recipient is assigned to polyTreg and the recipient does not receive intended polyTreg infusion, that recipient will be reassigned to Group 1. The allocation schedule algorithm/scheme will not incorporate stratification variables.

4. Rationale for Study Population

Adult recipients of kidney transplants with stable graft function who are found to have inflammation with or without minor tubulitis on a 6-month surveillance biopsy will be eligible for the trial. Inflammation in the renal allograft is well-recognized as a predictor of long-term graft dysfunction and graft loss ((Park WD, 2010); (Mannon RB M. A., 2010)). Patients who are found to have inflammation on the 6-month surveillance biopsy have already received maximal treatment with induction therapy and are maintained on dual or triple immunosuppression, so more intense therapy may not control the inflammation and is often associated with drug-induced toxicities. Currently, these patients do not receive any specific intervention to treat the inflammation despite the future risk of graft dysfunction. These patients are therefore excellent candidates for immunomodulatory therapy that can alter the balance of the immune system towards a more regulatory phenotype and lead to better long-term function.

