15.3.1. Analysis Samples

The statistical analyses will be performed on the following subject samples:

1. The Modified Intent-to-Treat Sample 1 (mITT1) consists of all subjects allocated to the CNI-based treatment regimen or received polyTregs while on study.
2. The Per Protocol Sample (PP) consists of all subjects allocated to the CNI-based treatment regimen or received at least 300×10^6 of polyTregs while on study that did not have major protocol deviations of concern.
3. The modified intent-to-Treat Sample 2 (mITT2) consists of all subjects who received polyTregs (Group 2).

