Although the study is not powered to detect clinically significant differences in safety event incidence between treatment groups, in a supportive analysis, the incidence of the composite endpoint will be compared between the two treatment groups by an overall Fisher's exact test using the miITT1 analysis sample to compare the incidence between the two groups.

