15.3.2.3 Primary Efficacy Endpoint

The primary efficacy endpoint is the mean change from baseline in percent inflammation on biopsy at 7 months and it will be compared between the two treatment groups by ANOVA using the mITT1 analysis sample. The primary endpoint data will be summarized in the 2 groups using boxplots, along with means and 95% confidence intervals.

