15.3.2.5 Supportive Analyses of the Primary Efficacy Endpoints

In addition to the primary efficacy endpoint analysis described above, several supportive analyses will be performed:

1. Since the occurrence of treated rejection prior to or at the time of the 7 month biopsy may confound the measurement of inflammation, the ANOVA described above will be repeated deleting any subjects from the analysis who had treated rejection prior to the 7 month biopsy.
2. Since clinical site, donor type, and race may confound the interpretation of the primary analysis, ANCOVA will be used to separately test for the effect of site, donor type, and race on the primary endpoint analysis.
3. If the PP sample differs from the mITT1 sample, the primary endpoint analysis will be repeated on the PP analysis sample.

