#### 4. ANALYSIS SAMPLES

**Modified Intent-to-Treat Sample 1 (mITT1)** – The mITT1 sample consists of all subjects allocated to the CNI-based treatment regimen or received polyTregs while on study.

**Modified intent-to-Treat Sample 2 (mITT2)** – The mITT2 sample consists of all subjects who received polyTregs (Group 2).

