### **6.2. Randomization**

Participants will be assigned to the treatment groups in an unblinded fashion using a variation of the Pocock and Simon adaptive randomization strategy. A web-based randomization system will be used in order to minimize the possibility of bias entering into those assignments and to maintain approximate equality in the group sizes. The initial treatment allocation will weight each treatment equally. In subsequent allocations, the less-populated arm will be weighted more in order to restore the balance between the groups. If a recipient is assigned to polyTreg and the recipient does not receive the intended polyTreg infusion, that recipient will be re-assigned to Group 1. The allocation schedule algorithm/scheme will not incorporate stratification variables.

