### **8.1.2. Primary Analysis of the Primary Endpoint**

The ANOVA method or Kruskal-Wallis test (or t-test for comparison of Groups 1 and 2) will be used to compare treatment groups on the mean or median percent change in inflammation at 7 months post-group allocation, relative to baseline biopsy. This method will be run on the mITT1 population, subset to participants that have available LCA data from the 7 month visit post-group allocation.

The Fisher's Exact or Cochran-Mantel-Haenszel tests will be used to compare the treatment groups on the incidence of severe acute cell-mediated rejection and/or acute antibody mediated rejection. This method will be run on the mITT1 population, subset to participants that have available Banff data.

The ANOVA method or Kruskal-Wallis test (or t-test for comparison of Groups 1 and 2) will be used to compare treatment groups on the mean or median time of event of severe acute cell-mediated rejection and/or acute antibody mediated rejection. This method will be run on the mITT1 population, subset to participants that have available Banff data.

The Fisher's Exact or Cochran-Mantel-Haenszel tests method will be used to compare the treatment groups on the incidence of severe infection. This method will be run on the mITT1 population.

The ANOVA method or Kruskal-Wallis test (or t-test for comparison of Groups 1 and 2) will be used to compare treatment groups on the mean or median time of event of severe infection. This method will be run on the mITT1 population.

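### Non-infused polyTreg participants are reassigned to Group 1 and mITT1 defines Group 2 by infusion, so any non-infusion breaks the randomised comparison, and no as-randomised analysis is pre-specified

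*Protocol*

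**What the plan says.** Protocol 3.7 describes a 1:1 adaptive allocation and then adds: "If a recipient is assigned to polyTreg and the recipient does not receive intended polyTreg infusion, that recipient will be reassigned to Group 1". SAP 6.2 keeps the rule ("that recipient will be re-assigned to Group 1").

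The main analysis sample is built differently for the two groups. Protocol 15.3.1 says that mITT1 "consists of all subjects allocated to the CNI-based treatment regimen or received polyTregs while on study", and SAP 4 has the same definition. Group 1 enters by allocation and Group 2 by infusion.

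mITT1 is used for every primary comparison:
- Efficacy, protocol 15.3.2.3: "it will be compared between the two treatment groups by ANOVA using the mITT1 analysis sample".
- Efficacy, SAP 8.1.2: "This method will be run on the mITT1 population, subset to participants that have available LCA data from the 7 month visit post-group allocation".
- Safety: protocol Table 7 assigns both primary incidences to this sample. The Fisher test in protocol 15.3.2.2 is run "using the miITT1 analysis sample to compare the incidence between the two groups". SAP 8.1.2 does the same, with the rejection endpoint limited to those with Banff data.

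The only other sample for the primary efficacy endpoint is per protocol (15.3.2.5: "the primary endpoint analysis will be repeated on the PP analysis sample"). It also takes Group 2 by cells received, at least 300 × 10^6. SAP 8.1.3 and 8.1.4 plan no sensitivity or secondary analysis of the primary endpoint. The SAP abbreviation list contains an ITT sample, but SAP 4 defines only mITT1 and mITT2.

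**The concern.** Randomisation protects a comparison only if group membership is fixed when it happens. Here membership of Group 2 depends on a later event, and those who fail to reach that event are added to the comparator.

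Non-infusion is foreseen. Protocol 4.2.2 bars infusion of an unacceptable product. Protocol 4.2.1 requires the enrolment criteria still to hold, 10.3.2 has this reviewed at the infusion visit, and 10.6 allows infusion up to day 62 after central pathology confirmation. Some reasons for non-infusion may therefore relate to the patient's condition, and sites are not blinded.

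The plan also does not settle who stays. Section 3.7 reassigns the non-infused, 13.1 allows termination after two manufacturing failures in one subject, and 13.2 replaces those terminated before infusion. Nor is it stated whether *allocated* in mITT1 means original or revised allocation. On the first meaning a non-infused participant leaves the primary comparison. On the second, that participant becomes a control. Neither gives the randomised comparison.

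With 14 participants, the group label of one person can change a reported result.

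**Working it through.** **Inputs.** From protocol 15.5: 7 per group, two-sided alpha 0.05, and the Table 11 case of a 30-point difference with SD 15. The following are assumptions, not in the documents: k participants randomised to polyTregs are not infused; people of that type have a 7-month percent change worse by s points; the type is equally common among controls; there is no true effect.

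**Plan's own figure.** The two-sample t-test with 7 vs 7, difference 30, SD 15 and 12 degrees of freedom gives power 92.9%, as in Table 11.

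**Are k = 2 or 3 compatible with the stopping rules (protocol 13.3)?** Three subjects failing twice make 3 × 2 = 6 failed lots, below the limit of 8 if no other lot fails. At positions 1, 2 and 6 of 7, no run of five consecutive subjects contains more than two of them.

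**Expected false benefit.**
- Reassigned, no rebalancing (7−k infused vs 7+k). Group 1 holds k reassigned plus, on average, k of that type among the 7 controls. Bias = 2ks/(7+k).
- Reassigned, arms rebalanced to 7 infused vs 7. Of 7+k randomised to polyTregs, k are not infused, so the share of that type is k/(7+k). Group 1 is k reassigned plus 7−k controls. Bias = s[k + (7−k)k/(7+k)]/7 = 2ks/(7+k), the same.
- Original-allocation reading, not replaced (7−k vs 7). Bias = ks/7.
- Terminated and replaced (7 infused vs 7 randomised to CNI). Bias = ks/(7+k).
- As randomised. Bias = 0.

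The table gives points of false benefit. In brackets is the simulated chance of a significant result favouring polyTregs, against 2.5% nominal (pooled t-test, 400,000 runs).

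| Configuration | k=2, s=15 | k=2, s=30 | k=3, s=15 | k=3, s=30 |
|---|---|---|---|---|
| Reassigned, 7−k vs 7+k | 6.7 (9%) | 13.3 (17%) | 9.0 (12%) | 18.0 (26%) |
| Reassigned, rebalanced 7 vs 7 | 6.7 (10%) | 13.3 (21%) | 9.0 (16%) | 18.0 (37%) |
| Dropped, 7−k vs 7 | 4.3 (6%) | 8.6 (9%) | 6.4 (8%) | 12.9 (13%) |
| Replaced, 7 vs 7 | 3.3 (5%) | 6.7 (9%) | 4.5 (7%) | 9.0 (13%) |
| As randomised | 0 (at most 2.6%) | 0 | 0 | 0 |

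Example: k=3, s=30, reassigned: 2 × 3 × 30 / 10 = 18.0. For k=1 with reassignment the bias is 2 × 15 / 8 = 3.75 to 2 × 30 / 8 = 7.5 points (about 5 to 8%). With s=0 every row is zero; with s negative the sign reverses.

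**Safety illustration, 7 randomised per arm, no rebalancing.** Take one pre-infusion event that blocks infusion and no other event. As randomised it is 1/7 vs 0/7 (+14 points). After reassignment it is 0/6 vs 1/8 (−12.5 points). If the participant drops out it is 0/6 vs 0/7.

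**The case against.** Several points on the other side stand in part.

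- **Traceability.** A reader might infer that the shift would be invisible. The documents do not support that. SAP 5.1 reports disposition with reasons for stopping treatment, SAP 9.3 and 9.4 list AEs and SAEs, and SAP 9.2 allows a listing of infusion status if regulatory reporting needs it. With 14 people, individual cases could largely be traced. What these outputs do not give is a pre-specified as-randomised comparison.
- **Group sizes.** The design aims for 7 infused (synopsis, 3.1), weights later allocations towards the smaller arm (3.7) and replaces those terminated before infusion (13.2). So 7−k vs 7+k is only one possible end state. Rebalancing leaves the bias unchanged and raises the error rate. Replacement halves the bias.
- **Prognosis.** The explicit provisions on failure to infuse are mostly about manufacturing, and nothing in the documents links expansion failure to later inflammation. The 15 to 30 point deficit is therefore an assumption, and it drives every efficacy figure.
- **Safety.** An event before any cells are given cannot be caused by them, so counting it in the polyTreg arm is not the only defensible display. That rejection or infection would block infusion is itself partly inferred. Counting such an event as a control event is still hard to defend.
- **Existing analysis.** Protocol 15.3.2.5 repeats the ANOVA without subjects who had treated rejection before the 7-month biopsy. This removes one prognosis-linked case, but the SAP does not carry it forward.
- **Purpose.** This is a pilot, and SAP 7.1.4 calls the analysis mainly descriptive. That limits the weight of the error rates. It does not make the groups as randomised.

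**Conclusion.** The concern holds in conditional form. If any participant randomised to polyTregs is not infused, the primary efficacy and safety comparisons on mITT1 are not between the randomised groups, whichever way *allocated* is read, and no planned analysis supplies the as-randomised comparison.

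The size is illustrative only. At k = 2 to 3, s = 15 to 30, SD 15 and no true effect, false benefit is about 6.7 to 18.0 points with reassignment. The favourable-tail error is then about 9 to 26% without rebalancing and about 10 to 37% with it. If the non-infused are terminated and replaced, the figures are about 3.3 to 9.0 points and about 5 to 13%.

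A reader might go further and infer that the trial's result is biased, or biased towards polyTregs. The documents do not support this. They do not say how many were not infused or how they fared. There is no departure if everyone is infused, no efficacy bias if non-infusion is unrelated to outcome, and a bias against polyTregs if the non-infused do better.

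**What to change.** 1. Remove the reassignment for analysis purposes from protocol 3.7 and SAP 6.2.
2. In protocol 15.3.1 and SAP 4, define Group 1 of mITT1 as participants randomised to CNI, and label mITT1 as infused versus randomised control. This alone is not enough, as the dropped and replaced rows of the table show.
3. Define the ITT sample that the SAP abbreviates as all participants randomised to CNI or polyTregs, by original allocation, including any later replaced.
4. On that sample, report the 7-month percent change and both primary safety incidences beside mITT1, with the number lacking a 7-month biopsy by arm.
5. List non-infused participants separately, with reasons and pre-infusion events, and never count those as control events.
6. Reconcile protocol 3.7, 13.1 and 13.2 on who is reassigned, terminated or replaced.

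**Cost.** Wording, and one extra analysis per primary endpoint. Participants who stay on study need no new procedure, because the one-year biopsy is standard of care (protocol 8.3).

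The as-randomised analysis has less power. With a 30-point effect in the infused, none in the non-infused and SD 15, simulated power falls from 92.9% to about 76%, 53% or 32% when 1, 2 or 3 of 7 are not infused. The expected difference is 30 × (7−k)/7 = 25.7, 21.4 or 17.1 points, and mixing the two types also widens the spread in that arm. Limiting Group 1 to those randomised to CNI (7−k vs 7) gives mITT1 power of about 90%, 87% or 81%, against 92%, 91% or 87% with the reassigned added. With this little power, the as-randomised result should be read mainly as an estimate with its interval.
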